Facebook may be an efficient platform for delivering evidence-based weight loss programming to post-partum women. Facebook is currently the most popular online social network,²⁰ used by 81% of online moms.²¹ 70% of Facebook users engage daily, including 43% multiple times per day,²² for upwards of 50 minutes a day.²³ Many women seek support about health and parenting from their Facebook network.^{21,24} Interactions via Facebook are frequent, brief, and asynchronous, with women seeking support when they need it. Delivering interventions via Facebook allows us to connect with post-partum women where they are, more fully integrating into their lives and daily routines. Weight loss interventions that use Facebook appear promising.²⁵⁻²⁷

We have developed a post-partum weight loss intervention based on the Diabetes Prevention Program,²⁸ tailored to needs of post-partum women and for delivery via Facebook. Participants receive counseling from a coach through posts and discussions via a private Facebook group. We conducted a one-arm pilot study of this intervention with 19 overweight or obese women (95% retention). Average weight loss was 4.8% (SD: 4.2%), and 58% achieved clinically significant weight loss (i.e., $\geq 5\%$).^{29,30} 88% said they would be likely/very likely to participate again if they had another baby, and 82% would recommend the program to a post-partum friend. While delivering the intervention via Facebook offers many advantages, we have no reason to believe it will be more efficacious than a traditionally-delivered intervention (i.e., via in-person group sessions), especially when intervention content is identical. Instead, we hypothesize that in a large trial delivery via Facebook will be at least non-inferior for weight loss compared to in-person delivery, but superior in cost-effectiveness.

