The main purpose of the pilot trial is to examine the feasibility of recruitment (especially the proportion of women unwilling to be randomized to either condition), sustained participation, contamination, retention, and feasibility of assessment procedures, particularly measurement of cost-related data, in both treatment conditions, thus identifying modifications required before examining non-inferiority in a large randomized controlled trial. Leon, Davis, & Kraemer (2011) state "power analyses should not be presented in an application for a pilot study that does not propose inferential results."³¹ As they and others recommend,^{31,32} we based the sample size on necessities for examining feasibility, thus identifying modifications required to the design of the trial or study procedures before conducting the subsequent full-scale non-inferiority trial. Conducting two waves allows us to iteratively refine how we deliver intervention content via Facebook, and each wave includes n=36 women allows us to assess the feasibility of recruitment and engagement under the conditions of the subsequent trial. While we will aim to maximize retention in both conditions, with retention of $\geq 80\%$ to be acceptable, a priori, we decided that a retention rate in either condition lower than 60% would indicate that the non-inferiority trial is not feasible as designed. With n=36 per treatment condition, the 95% confidence interval (CI) for the estimated retention rate will be within $\pm 13\%$ if observed retention is 80%. Given n=36 per condition, the lower limit of the 95% CI for the observed retention rate in either treatment condition should not be lower than 60%.

We will enroll up to 125 participants with the intention of randomizing 72 participants. As the current study is a feasibility study, we are unsure the proportion of enrolled (consented) participants who will be randomized, as some participants will fail to complete baseline measures or may be found to be ineligible after baseline assessments.

For EACH Participant Population State Describe the Study Population(s): [Describe the participant population(s) including gender, ethnicity, income, level of education and age range.]

All participants will be adult women (aged 18 years or older). We anticipate minority enrollment of at least 30% as expected by the NIH/NHLBI. We are not targeting enrollment by income or level of education; we aim to recruit a diverse sample with respect to these characteristics.

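### Does the sample-size section wrongly promise that 36 women per condition alone keep the lower 95% limit for retention at 60% or above?

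*Protocol*

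**What the plan says.** The relevant text is one paragraph in the protocol's Justification of Sample Size. It calls retention of 80% or more acceptable, and then sets a feasibility rule in advance: "a retention rate in either condition lower than 60% would indicate that the non-inferiority trial is not feasible as designed". The precision argument follows: "With n=36 per treatment condition, the 95% confidence interval (CI) for the estimated retention rate will be within" ±13%, on the condition "if observed retention is 80" percent. The closing sentence begins from the sample size per condition and says that "the lower limit of the 95% CI for the observed retention rate in either treatment condition should not be lower than 60" percent.

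Under Data Analysis, Aim 1, the protocol defines retention as the proportion completing the 6- and 12-month visits in each condition, to be shown in a CONSORT diagram. The SAP (Primary Outcomes: Feasibility, Retention) says only that retention will be reported by condition and that reasons for drop-out will be explored if it is lower than expected. Neither section names a confidence interval or a threshold for one.

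**The concern.** The closing sentence names the sample size as its only premise and mentions no observed rate. Taken literally, it says that 36 women per condition are enough to keep the lower limit at 60% or above, and no sample size can do that.

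The protocol's own rule supplies counterexamples. Between 22 and 26 retained out of 36 (61.1% to 72.2%), a condition is not below 60% on the observed rate, yet its lower limit is below 60%.

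The sentence is also the stated link between 36 per condition and the 60% threshold for a primary feasibility outcome. If it failed, the paragraph would overstate what the design can show. A reader might also take it as a second, stricter criterion on the lower limit, which those same counts would fail while passing the stated rule.

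**Working it through.** **Inputs.** From the Justification of Sample Size: n = 36 per condition, 95% confidence, observed retention p = 0.80, threshold 60%. The interval method is not named. Wald is assumed first because it gives the stated ±13%; Wilson and exact (Clopper-Pearson) limits serve as checks. Intervals are two-sided, z = 1.96.

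**Step 1: reproduce the plan's figure.** The Wald half-width is z·√(p(1−p)/n) = 1.96 × √(0.8 × 0.2 / 36) = 0.1307, or 13.07 points. The stated ±13% is right.

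**Step 2: lower limit at 80% observed retention.**

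- Wald: 0.800 − 0.131 = 66.9%.
- Wilson: [p + z²/(2n) − z·√(p(1−p)/n + z²/(4n²))] / (1 + z²/n) = (0.8000 + 0.0534 − 0.1411) / 1.1067 = 64.4%.
- Exact: the 2.5% quantile of Beta(x, n − x + 1), with x = 0.8 × 36 = 28.8, is 63.3%.

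The smallest whole count at or above 80% is 29/36 (80.6%), where the limits are 67.6%, 65.0% and 64.0%. The limit rises with the count, so the sentence holds for every result that the protocol calls acceptable.

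**Step 3: where it stops holding.**

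| Retained | Observed | Wald | Wilson | Exact |
|---|---|---|---|---|
| 22/36 | 61.1% | 45.2% | 44.9% | 43.5% |
| 26/36 | 72.2% | 57.6% | 56.0% | 54.8% |
| 27/36 | 75.0% | 60.9% | 58.9% | 57.8% |
| 28/36 | 77.8% | 64.2% | 61.9% | 60.8% |

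The lower limit first reaches 60% at 27/36 by Wald and at 28/36 by Wilson or exact. All the counterexamples (22 to 26 retained) lie below the 80% for which the precision is stated.

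**Step 4: what uses the limit.** The feasibility rule applies to the observed rate. Since 0.60 × 36 = 21.6, it is triggered by 21 or fewer retained in either condition. Whether 22 to 26 retained gives a lower limit of 45% or 58% does not enter that rule, and no other rule in the protocol or SAP refers to the limit.

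**The case for a change.** The strongest case for a change is that the closing sentence opens with its own premise, the sample size, and does not refer back to 80%. The protocol treats 80% as an acceptable level, not as an assured result. If true retention were 80% in both conditions (assuming 36 in each, and independence), the chance that both lower limits reach 60% would be 0.832² = 69% by Wald and 0.716² = 51% by Wilson or exact. At 75% true retention it would be 35% and 19%; at 90%, 99.6% and 98.5%. The team's pilot retained 95% of 19 women, but it had one arm and was delivered only through Facebook. Taken as 18/19, its exact 95% interval runs from 74.0% to 99.9%, so it does not exclude the less favourable cases and says nothing about in-person retention.

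The arithmetic stands, and so does the observation that the condition is not repeated. But these probabilities describe how often a given count would be reached under assumed true rates; they do not show the sentence to be wrong at 80% observed. The two sentences are adjacent ("if observed retention is 80%. Given n=36 per condition, the lower limit of the 95% CI") and form one argument. Because no sample size can guarantee a lower limit whatever is observed, the literal reading is not one that a statistician would adopt.

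The wording could also express a target for the lower limit. The text does not call it a criterion, and the explicit rule in the same paragraph is set on the rate.

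**Conclusion.** The concern does not call for a change. The closing sentence omits a condition that the sentence before it supplies. With the condition in place it is correct, with 3 to 7 points to spare over 60% depending on the method (63.3% exact, 64.4% Wilson, 66.9% Wald). The ±13% figure, the 36 per condition and the 60% rule on the observed rate all stand.

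This rests on two readings: that 80% carries over from one sentence to the next, and that the no-go rule applies to the observed rate, as written. If the first is refused, the limit reaches 60% only from 27 or 28 retained out of 36, but even then nothing downstream changes. Retention is reported descriptively by condition, and anyone computing an interval will use the observed count. This is a drafting omission with no effect on the design, the analysis or the feasibility decision.

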Additional preliminary data is needed to support the conduct of a large randomized non-inferiority trial to compare our Facebook-delivered post-partum weight loss intervention to in-person delivery of the intervention. In our pilot study, some intervention posts garnered low or no participant engagement. We have identified posts with low and high participant engagement, and will solicit feedback from women on how to make low engagement posts more engaging. As noted in the grant proposal (Section 3.B/Impact), the research described in this protocol is a step in a line of investigation to develop and test the efficacy and effectiveness of a Facebook-delivered post-partum weight loss intervention. Subsequent steps of this program of research include implementation in real-world settings. It is possible that the best model for widespread dissemination would be to develop a commercial product.

This project has three Specific Aims:

Aim 1: Feasibility. We will examine the feasibility of recruitment (especially the proportion of women unwilling to be randomized to either condition), sustained participation, contamination, retention, and

feasibility of assessment procedures, particularly measurement of cost-related data, in both treatment conditions. We will describe weight loss as an exploratory outcome.

Aim 2: Intervention refinement. In post-intervention focus groups, we will solicit women's feedback on posts with low engagement, and will iteratively refine these posts to make them more engaging.

Aim 3: Measuring time on Facebook. We will compare self-reported time spent on Facebook to participate in the intervention with application-tracked time on Facebook, changes in use, and time spent visibly engaging, to develop procedures for measuring time that balance accuracy and participant burden.

Please see the Specific Aims (page 1) and sections 3.A through 3.D.1.5 of the enclosed grant application (pages 2-7) for additional background information supporting the proposed research. The current protocol will cover research activities described as Phase 2 in the grant application; a separate protocol covers research activities described as Phase 1 (IRB # H17-203).

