Design, Procedures, Materials and Methods: [Describe the study design, including the sequence and timing of all study procedures. Experimental procedures should be clearly described and labeled as such. If the study uses control or experimental groups, or different treatment arms, clearly describe what participation will be like for each of the groups or study arms. Tip: describe procedures in the order conducted. The IRB strongly suggests that investigators incorporate *flexibility* into the study design to accommodate anticipated events (i.e. explain how missed study appointments can be made up by participants). If the research involves study of *existing samples/records*, describe how authorization to access samples/records will be obtained. If the study involves use of *deception* explain the reason why this is necessary. If applicable, describe the use of audiotape and/or videotape and provide justification for use. If this study offers treatment for the participants’ condition, complete the Treatment Study Supplemental Form (IRB-1C) and attach it to this application for review. If the study includes *measures, survey instruments and questionnaires*, identify each and, if available, provide references for the measures. Describe what they intend to measure (relate to purpose/hypothesis) and their psychometric properties (e.g., reliability and validity). Identify any that were specifically created for the study.]

Participation will include a baseline assessment, an orientation webinar, participation in a 6-month weight loss intervention, and follow-up assessments at 6 and 12 months. Study visits and in-person treatment sessions will take place in a private space (such as a conference room, exam room, or classroom) at UConn Storrs, UConn Hartford, the Hartford Public Library, Hartford Hospital, Women’s Ambulatory Health Services, or WIC offices. Overall, it is estimated that completing study assessments will take approximately 5-6 hours and participating in treatment sessions (in-person condition) or engaging with

the counselor and other participants online (Facebook condition) will take approximately 90 minutes per week over the 6-month intervention period.

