Weight loss intervention. The 6-month intervention will include dietary and exercise counseling and tips to help participants meet their healthy lifestyle goals. Participants will receive personalized calorie and physical activity goals to help them achieve a healthy weight loss of 1-2 pounds per week. Breastfeeding women will receive daily calorie goals that will facilitate weight loss while accounting for energy needs to support lactation; weight loss expectations do not differ by breastfeeding status. Participants will be encouraged to increase physical activity to 150 minutes per week of moderate intensity activity. While we will provide information about specific exercises designed to help with recovery from childbirth (e.g., pelvic floor exercises), participants will not be required to engage in any particular exercises or activity program. Counselors will encourage and support participants to make a plan for incorporating regular physical activity into their lives in a way (i.e., duration per session, frequency per week) that works for that individual woman. We will encourage participants to track their diet and exercise daily. We will encourage participants to use My Fitness Pal to track their diet and activity. In the in-person condition, the intervention will be delivered via weekly 90-minute group meetings for the first four months and then every other week in months 5 and 6. In the Facebook condition, the intervention will be delivered via a secret (private) Facebook group. See section 3.D.2.2.9 (3.D.2.2.9.1 through 3.2.2.9.6; pages 9-10) of the enclosed grant application for more details on the interventions.

Due to weather or to prevent spread of illness (e.g., coronavirus), we may hold intervention meetings for the in-person condition via video or telephone conference call.

Weekly time survey. Weekly, participants in both treatment conditions will complete a brief online survey to report current weight and time spent on Facebook. We expect the survey to take less than 5 minutes. The survey will be administered via REDCap. A copy of the weekly survey is enclosed.

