Aim 3: Measuring time on Facebook. We will compare self-reported time spent on Facebook to participate in the intervention with application-tracked time on Facebook, changes in use, and time spent visibly engaging, to develop procedures for measuring time that balance accuracy and participant burden. We will compare self-reported time spent on Facebook to participate in the intervention with (1) application-tracked time spent on Facebook, (2) change in application-tracked time over the intervention, and (3) estimated time spent visibly engaging in the intervention using paired t-tests and Wilcoxon rank-sum tests, as appropriate. We will also examine accuracy in reporting total time on Facebook at baseline and adjust self-reported time spent on Facebook to participate in the intervention accordingly. From these comparisons, we will develop procedures for measuring time spent on Facebook to participate in the intervention that maximize accuracy while not placing undue burden on participants nor changing their behavior as a result of surveilling their social media activities.

Inclusion/Exclusion Criteria: [List ALL inclusion and exclusion criteria. Any proposed exclusion criterion based on gender (women of childbearing potential), age, or race must include justification for the exclusion. Describe the conditions under which participants may be removed from the study, i.e., noncompliance with study rules, study termination, etc.]

Only women will be included as the aim of this study is to refine a post-partum weight loss intervention.

Inclusion criteria. Women aged ≥ 18 years, 8 weeks to 12 months post-partum at enrollment, overweight or obese ($BMI \geq 25$ kg/m²) per measured height and weight at the baseline visit, owns a scale (we will provide women with a scale if needed), comfortable reading and speaking English, owns an iPhone or Android smartphone, active Facebook user as defined as daily Facebook use and posts/comments at least weekly over the past 4 weeks, clearance from primary care provider or obstetrician/gynecologist, willing and able to participate in either treatment condition (Facebook or in-person), available to attend in-person meetings over the 6-month study period in Hartford, CT, 45 minutes or less to travel to intervention meetings, and willing and able to provide informed consent.

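### Aim 3 does not say how repeated weekly Facebook-time reports enter its two-measure tests, and those tests do not inform how often women should be asked

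*Protocol*

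**What the plan says.** Under Design, Procedures, Materials and Methods (Weekly time survey), the Protocol states: "Weekly, participants in both treatment conditions will complete a brief online survey to report current weight and time spent on Facebook". It adds: "We expect the survey to take less than 5 minutes". The study includes "participation in a 6-month weight loss intervention, and follow-up assessments at 6 and 12 months", but neither the number of weekly surveys nor their stop date is given.

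The purpose of Aim 3 is "to develop procedures for measuring time that balance accuracy and participant burden". Under Data Analysis, Aim 3 sets self-reported intervention time against three comparators: Facebook time recorded by an app, the shift in that recorded time during the programme, and an estimate of time spent in visible activity. The comparisons are to be made "using paired t-tests and Wilcoxon rank-sum tests, as appropriate". The Protocol then says: "From these comparisons, we will develop procedures for measuring time spent on Facebook to participate in the intervention". The same sentence goes on to ask for accuracy without excessive burden and without altering behaviour through monitoring.

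The SAP, under Feasibility of assessment procedures, repeats the goal of developing a way to assess Facebook time and plans a review of missing data. It names no method for Aim 3.

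**The concern.** A paired t-test takes one independent pair per woman, while the design can produce many weekly values per woman. The plan does not say how the many become one. Even under the sensible choice, one average per woman, the result is only a mean difference between two ways of measuring time.

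That speaks to average accuracy. It does not show how much a woman's time varies from week to week compared with how much women differ from each other, and that split determines whether weekly reporting is needed or a sparser schedule would do. Burden in Aim 3 also covers which method to use and whether monitoring changes behaviour, so frequency is only part of it. It is a part on which the weekly data could give direct evidence, and no stated analysis extracts that evidence. The later trial's reporting schedule, which feeds its cost-effectiveness aim, would then be set without it.

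**Working it through.** **Figures in the plan.** Neither document gives a precision figure for Aim 3. The only one in the Protocol concerns retention, under Justification of Sample Size: "With n=36 per treatment condition, the 95% confidence interval (CI) for the estimated retention rate will be within" ±13% if observed retention is 80%. It reproduces: 1.96 × √(0.8 × 0.2 / 36) = 0.131. It is used here only as the source for 36 women per condition.

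**Inputs**
- Women giving intervention-related Facebook time: at most 36 (Protocol, Justification of Sample Size).
- Weekly reports per woman: 26, an assumption from the 6-month duration.
- Correlation between two weeks in the same woman, ρ: not given. Assumed 0.5, range 0.3 to 0.7, with 0.2 and 0.8 as wider checks.
- Full completion, and weeks equally correlated within a woman: assumptions.

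**Case A: one average per woman.** In a simulation of 36 women by 26 weeks (4,000 runs, no true difference), the nominal 5% paired t-test on per-woman means rejected in 5.4%, 5.1% and 4.6% of runs at ρ = 0.2, 0.5 and 0.8. The test is valid, but its output contains no variance split.

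That split matters because the reliability of a woman's mean over k reports is kρ / (1 + (k − 1)ρ). The standard error of the arm's mean from k reports, relative to 26, is √[(ρ + (1 − ρ)/k) / (ρ + (1 − ρ)/26)]. Every second week gives k = 13. Every fourth week gives k = 7 (weeks 1, 5, …, 25).

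| ρ | Reliability, k = 26 | k = 13 | k = 7 | SE ratio, 13 vs 26 | SE ratio, 7 vs 26 |
|---|---|---|---|---|---|
| 0.3 | 0.918 | 0.848 | 0.750 | 1.040 | 1.106 |
| 0.5 | 0.963 | 0.929 | 0.875 | 1.018 | 1.049 |
| 0.7 | 0.984 | 0.968 | 0.942 | 1.008 | 1.022 |

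Worked at ρ = 0.5, k = 7: reliability is 3.5 / 4 = 0.875, and the SE ratio is √(0.5714 / 0.5192) = 1.049.

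Solving for reliability 0.80, k = 0.8(1 − ρ) / (0.2ρ), rounded up where needed, gives 16, 10, 4, 2 and 1 reports at ρ = 0.2, 0.3, 0.5, 0.7 and 0.8. The answer therefore ranges from one report to 16, depending on a quantity the plan does not estimate.

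On the burden side, at up to 5 minutes per survey, 26 surveys take up to 26 × 5 = 130 minutes per woman and 7 take up to 7 × 5 = 35. The survey also collects weight, so the saving from dropping only the time question would be smaller.

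**Case B: woman-weeks pooled (not stated in the plan).** There would be 36 × 26 = 936 pairs. The design effect is 1 + 25ρ = 8.5, 13.5 and 18.5 at ρ = 0.3, 0.5 and 0.7. Standard errors would be too small by the square roots: 2.9, 3.7 and 4.3. In the same simulation the nominal 5% test rejected in about 43%, 60% and 68% of runs at ρ = 0.2, 0.5 and 0.8.

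**The case against.** A reader might infer that Aim 3 ignores the repeated weeks and that its burden question cannot be answered. The documents do not support either reading.

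- Nothing says woman-weeks will be pooled. The plan is silent on aggregation, averaging per woman keeps the paired t-test valid, and one comparator already involves change over time. The 3.7-fold figure describes a choice the plan does not make.
- Burden is not defined as the number of reports. Aim 3 reads at least as naturally as a choice between self-report and app tracking, with reactivity in mind, and the planned comparisons do address that choice.
- The limitation lies in the named tests, not in the study. The weekly data would support the missing analysis, and the SAP's missing-data review gives some indirect evidence on burden.

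All three points stand. So do some cautions about the data. The weekly survey form and the grant application are enclosures that were not available here, so it cannot be confirmed that intervention-specific time and app-recorded time are both captured every week. Equally correlated weeks are doubtful if engagement declines. Self-report of intervention time minus app-recorded total Facebook time is a difference, not an error. Thinning one-week reports cannot show how well women would recall a longer period.

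It may also be said that a feasibility pilot needs no more than this. But Aim 3 is a specific aim whose product is a measuring procedure, and the Protocol says that product will come from these comparisons. None of the objections supplies an analysis that bears directly on how often to ask.

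**Conclusion.** The point holds in a limited form. Aim 3 leaves the route from weekly values to a two-measure test unstated. Under the valid route, it yields a mean difference without the variance split needed to inform reporting frequency.

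Under the assumptions above, reporting every fourth week instead of weekly would widen the standard error of the arm's mean time by about 5% (2% to 11% for ρ from 0.7 to 0.3). The reliability of an individual woman's mean would fall from 0.96 to 0.88 at ρ = 0.5, and from 0.92 to 0.75 at ρ = 0.3. These figures are illustrations, not predictions: one assumed correlation stands in for both weekly times and weekly differences, whose correlations may differ. Inflated false-positive rates would arise only if woman-weeks were pooled as independent.

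**What to change.** Amend Aim 3 in the Protocol's Data Analysis section, and carry it into the SAP:

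1. State that the woman is the independent unit.
2. Analyse weekly differences (self-report minus comparator, using weeks with both values, as far as the weekly form allows) in a linear mixed model with a random effect for woman and week as a fixed effect, to allow for drift.
3. Report the mean difference, the between-woman SD and the within-woman SD. Do not call the difference an error where the comparator is total Facebook time.
4. Add a descriptive comparison of each woman's mean from every second and every fourth weekly report with the mean of her full series. Use it as one input to the later trial's reporting schedule, noting that it tests neither longer recall periods nor reactivity.

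While the sentence is being edited, note that the rank-sum test is for independent samples; the signed-rank test is its counterpart for paired values.

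The cost is some wording and a little more analysis in SAS. No new data are needed and participants do nothing extra.
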